9.2 Outcome Analysis

Eligible participants will enter the study within 45 days of screening as eligible and will be followed longitudinally for PrEP uptake for up to 12 months. Analyses will be conducted for all primary and secondary outcomes defined in Table 3 (Section 7.0) using the following general procedures for analysis.

Basic descriptive statistics will be calculated. Frequency tables will be presented for the categorical variables and means, standard deviations, and percentiles (25th, 50th, 75th) will be given for the continuous variables. For each binary outcome, we will estimate the proportion of patients achieving the event (e.g., PrEP uptake) in each arm and a probability difference (PD) and a corresponding 95% confidence interval (CI) to compare the intervention vs. control arms at each timepoint (3-month, 6-month, and 12-month follow-up). For continuous endpoints, we will use a non-parametric Wilcoxon Rank-Sum Test to compare the intervention and control arms. For count

data variables (e.g., number of unprotected sex acts), we will use small analysis methods for count data (e.g. exact Poisson regression).

To address missing data, we will review the frequency of missing and non-missing values for all variables at baseline, 3-month, 6-month, and 12-month follow-up. We will conduct missing value analyses to determine whether persons with missing values are systematically different from those without missing values and if the probability of having missing values differs by arm. If this assessment of the frequency and imbalance of missing data suggests that bias may be introduced, we will employ inverse probability of observation weights or multiple imputation to address the missing data.

If there is chance imbalance in the measured baseline covariates, we will conduct sensitivity analyses applying stabilized inverse probability treatment weights (IPTW).

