6.1 Study onboarding appointment and baseline assessment

[figure not shown]
All participants will complete an onboarding appointment via phone or HIPAA-compliant videoconferencing platform. Participants will be considered enrolled and be eligible for the enrollment completion incentive once the below activities are complete:

- Informed consent and HIPAA authorization. Receipt of a unique access link to complete their Baseline CASI survey capturing PrEP use history, sexual behaviors, demographics, and determinants of PrEP use (access to care, perceived HIV risk, social support, perceived discrimination, mental health, substance use, and PrEP decision making). The CASI survey is self-administered via secure HIPAA-compliant platform (e.g. RedCap) and participants can complete the survey on their personal device with internet, wi-fi or mobile data. The survey saves after every page thus participants can return to complete the survey if their connection is disrupted or for any other reason.
- Randomized to study condition.
- Receipt of a unique access code and directions to download their free designated version (intervention or control) of the HMP study app from either the Google Play or Apple store.
- Creating their unique HMP account profile and log-in; touring the app features.

The onboarding appointment for intervention participants will also include being connected to their assigned PrEP navigator.

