6.4 Follow-up study assessments

Follow-up study assessments will be conducted for all participants, including standard of care repeat HIV/STI testing³¹ and repeat self-administered CASI survey assessments, with the number of follow-up assessments dictated by timing of enrollment. The baseline questionnaire is distributed after a participant completes informed consent and before they are randomized. If the participant does not complete Informed Consent, HIPAA Authorization, the baseline questionnaire and baseline HIV status verification within 45 days of completing the screening questionnaire, the participant must re-screen to assess eligibility.

The follow-up period (described as the post-randomization phase) begins once participants have been randomized to a study condition. Randomization will occur once participants have connected with study staff for their onboarding appointment. An overview of the pre and post randomization assessments conducted in each study phase are described in Tables 2.1 – 2.3.

A subset of participants will be asked to complete a brief CASI survey pertaining to PrEP uptake and/or persistent use and self-reported STI or HIV testing outcomes at 12-months if this follow-up interval falls within the allowable data collection timeframe based on when a person was enrolled (see Section 17.0 Timeline). The study windows for each follow-up time

Table 2.1: Participant Assessment Timeline

| Pre-Randomization | | | |
|--|----------|-----------|------------------------------|
| Study Activity | Day Open | Day Close | Study Window Duration (days) |
| Screening Questionnaire | 0 | 45 | 45 |
| Informed Consent + HIPAA Authorization | 0 | 45 | 45 |

Table 2.2: Participant Assessment Timeline for Participants Followed 6 -12 Months

| Post-Randomization | | | |
|--|----------|-----------|------------------------------|
| Study Activity | Day Open | Day Close | Study Window Duration (days) |
| App Account Generation | 0 | 0 | 1 |
| Baseline STI Result Abstraction ¹ | 0 | 89 | 89 |
| Baseline HIV Result Abstraction ² | 0 | 45 | 45 |
| 3M Survey | 90 | 165 | 75 |
| 3M DBS | 75 | 165 | 90 |
| 3M HIV/STI Result Abstraction ¹ | 90 | 165 | 75 |
| 6M Survey | 166 | 196 | 30 |
| 6M DBS | 166 | 211 | 45 |
| 6M HIV/STI Result Abstraction ¹ | 166 | 276 | 110 |
| 12M Survey ³ | 365 | 440 | 75 |
| Qualitative Exit Interview ³ | 90 | 276 | 186 |

Table 2.3: Participant Assessment Timeline for Participant Followed for 3 Months

| Post-Randomization | | | |

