| PrEP adherence (self-report) | 3- and 6-month ⁴ follow-up | Daily oral PrEP : reported PrEP use (past 30 days) Event-driven PrEP : reported PrEP use corresponding to reported sexual activity (past 30 days) Injectable PrEP : based on date of injections | CASI |
| PrEP adherence (injection history & drug measurement) | 3- and 6-month ⁴ follow-up | Daily oral PrEP : PrEP concentrations detected at designated study follow-up visits, based on intraerythrocytic TFV-DP collected as DBS; Injectable PrEP : based on dates of injections | Self-collected lab sample, EHR |
| Incident STI/HIV | 3- and 6-month ⁴ follow-up | Clinical test result (yes / no / indeterminate / missing) for each STI and HIV that participant is tested for. | CASI; State, clinic, commercial lab results ³ |
| PrEP Stigma | 3- and 6-month ⁴ follow-up | Self-reported scored PrEP Stigma scale | CASI |
| Implementation measures (intervention arm and stakeholders) | | | |
| Fidelity-Engaged by PrEP navigator | First two weeks following enrollment | Proportion of Intervention Arm enrolled participants that are engaged by the PrEP navigator within two weeks of enrollment | Intervention CRF |
| Intervention satisfaction - Quantitative | 3- and 6-month ⁴ follow-up | Average score on participant-completed System Usability Scale (10 item universal measure of usability and acceptability). | CASI |
| Intervention satisfaction – Qualitative | 3- or 6-month ⁴ follow-up | Description of participant experiences and satisfaction, usefulness and attribution to PrEP use while on study and with each intervention component. | In-depth interviews with participants |
| Acceptability | Within 3-months before or after baseline and | Description of stakeholder experiences and acceptability of intervention, readiness for change, implementation | In-depth interviews and surveys with |

| | | | |
|--------------------------------|--|--|--|
| | within 3 months before or after study close-out | climate, and intervention values | stakeholders |
| Clinic measures | | | |
| STI service delivery | Baseline, 3- and 6-month ⁴ follow-up | Proportion of enrolled participants receiving STI screening (urogenital, rectal, pharyngeal) at baseline (pre-enrollment) and follow-up timepoints | State, clinic, commercial lab results ³ |

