9.0 STATISTICAL/ANALYTIC CONSIDERATIONS

9.1 Sample Size and Power Estimate

We expect > 7,400 patients will present for care in the 21-month enrollment period, with 20-35% study eligible. Aim 1 analysis includes eligible, consenting patients who successfully download the HMP app. The study will enroll for 21 months with a target sample size of 336. We expect approximately half of participants will be randomly assigned to the intervention arm and the remaining half to the control arm (see Randomization, Section 3.2).

We calculated statistical power for the effect of intervention upon PrEP uptake by 3-month follow-up using SAS 9.4 (Cary, NC) with a 5% type I error rate and a two-sided Chi-square test. Assuming 2.5% of eligible patients start PrEP within 3 months in the control arm, we calculated statistical power to detect a range of small to large effect sizes from 5% to 15% percentage point increases in PrEP uptake under a range of possible sample sizes and assuming 10% missing data (Table 4). At a total sample size of 336, given our design and assumptions, we will have >88% statistical power to detect medium (10%) and large (15%) effect sizes, and 80% statistical power to detect a moderate (7.5%) effect size.

Effect size rationale: As there is currently limited-to-no infrastructure or existing programming providing PrEP in rural North Carolina STI clinics, no prior studies that we are aware of have measured PrEP uptake in these settings. Overall, U.S. PrEP coverage of those assigned male sex at birth with PrEP indications was reported by CDC as 18.4% in January – March 2021, but only 5.6% among Black/African American⁴⁶, who will constitute a large portion of our sample. Among the CDC-designated End-the-Epidemic jurisdictions, recent PrEP coverage estimates of those with PrEP indications range from a low of 4.5% in San Bernardino to a high of 42.3% in San Francisco; North Carolina's state level PrEP coverage estimate is 13.3%, which belies the wide variability from

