9.2.2 Secondary Outcomes Analyses

Secondary effectiveness outcomes are listed in Table 3 (Section 7.0) including PrEP uptake at 6-months, and PrEP care engagement, PrEP use, PrEP adherence, incident STI/HIV, and PrEP stigma (at both 3- and 6-months, determined by when they are enrolled in the course of study enrollment). All analyses will follow the specifications described above in 9.2.

PrEP adherence at 3 and 6 months will be assessed using PrEP metabolite levels and self-report (3-month only for persons enrolled in approximately the final quarter of enrollment). We will use standard of care quarterly STI/HIV testing results to examine differential rates of incident STIs, adjusting for testing frequency given potential increased frequency among PrEP initiators.

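### PrEP stigma is compared by an unadjusted Wilcoxon test that ignores the county strata and any baseline score and gives no between-arm estimate with a confidence interval

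*Combined protocol and SAP*

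**What the plan says.** Table 3 in Section 7.0 lists PrEP stigma as a secondary outcome, a "Self-reported scored PrEP Stigma scale", with a time frame of 3 and 6 months. Section 9.2.2 names it among the secondary outcomes and adds: "All analyses will follow the specifications described above in 9.2".

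Section 9.2 has one rule for continuous endpoints: "For continuous endpoints, we will use a non-parametric Wilcoxon Rank-Sum Test to compare the intervention and control arms". It does not say whether the test is run on follow-up scores or on change, and it names no covariate or stratification factor. In the same paragraph, binary outcomes get a probability difference with a 95% CI. Continuous variables otherwise get only descriptive means, SDs and percentiles. Section 3.2 stratifies the randomization by county.

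The one step in 9.2 that uses baseline covariates depends on chance imbalance in them: "we will conduct sensitivity analyses applying stabilized inverse probability treatment weights (IPTW").

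On a baseline stigma score, the documents point both ways. Section 6.1 lists the content of the baseline survey. Apart from background items, the constructs named there are: "determinants of PrEP use (access to care, perceived HIV risk, social support, perceived discrimination, mental health, substance use, and PrEP decision making"). PrEP stigma is not on that list. Section 6.4 calls the follow-up surveys "repeat self-administered CASI survey assessments", and Section 9.2 plans to review missing values for all variables at baseline as well as at follow-up. Both suggest that the scale may be given at baseline, but neither says so.

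**The concern.** There are two separate gaps.

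The first is reporting. A rank-sum test gives a p-value. It does not say by how much stigma differs between arms, or how precisely that is known. Stigma matters to this trial's rationale: Section 1.0 lists it among the barriers to PrEP scale-up, Section 3.2.1 names it among the determinants that the app is built around, and Section 9.1 cites it when setting the expected effect on uptake. The Aim 3 refinement would need the size of any change in stigma, which a p-value cannot give. This gap exists whether or not a baseline score is collected.

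The second is efficiency. A two-sample rank-sum test cannot use the county strata or a pre-randomization score. Where a baseline score predicts the follow-up score, leaving it out keeps that variation in the error term. A real reduction in stigma is then more likely to be missed, and a chance baseline difference enters the main comparison uncorrected.

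**Working it through.** **No stated figure to reproduce.** The plan gives no power, SD, effect size or correlation for PrEP stigma. Everything below is conditional on assumptions, and the second and third steps apply only if a baseline stigma score exists.

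**Inputs from the documents (Sections 5.8 and 9.1)**
- Sample size: "The study will enroll for 21 months with a target sample size of 336". With 1:1 allocation this is 168 per arm.
- Missing data: 10% at month 3, stated for PrEP uptake. Carried over to stigma as an assumption: 168 × 0.90 = 151.2 per arm.
- Error rate: "with a 5% type I error rate and a two-sided Chi-square test", stated for the primary outcome. The two-sided 5% level is used here.

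**Inputs assumed**
- Standardized difference d from 0.20 to 0.40.
- Correlation ρ between baseline and follow-up scores from 0.3 to 0.7.
- Roughly normal scores, so the Wilcoxon test has relative efficiency 3/π = 0.955 against the t-test.

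**Formulas** (n per arm, Φ the standard normal distribution function)
- Unadjusted Wilcoxon: power = Φ( d·√(0.955·n/2) − 1.96 ).
- Rank-based adjustment: power = Φ( d·√(0.955·n/2) / √(1 − ρ²) − 1.96 ).
- ANCOVA: as the line above, without the factor 0.955.

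**Step 1: difference with 80% unadjusted power at 3 months.** √(0.955 × 151.2 / 2) = 8.50, and d = (1.96 + 0.84) / 8.50 = 0.33.

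**Step 2: adjusted power at that difference.**

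| ρ | 1 − ρ² | Rank-based adjustment | ANCOVA |
|---|---|---|---|
| 0.3 | 0.91 | 83.6% | 85.2% |
| 0.5 | 0.75 | 89.9% | 91.2% |
| 0.6 | 0.64 | 93.8% | 94.8% |
| 0.7 | 0.51 | 97.5% | 98.0% |

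Other effect sizes at 151.2 per arm and ρ = 0.5, Wilcoxon against ANCOVA:

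| d | Wilcoxon | ANCOVA | Gain (points) |
|---|---|---|---|
| 0.20 | 39.7% | 51.9% | 12 |
| 0.25 | 56.5% | 70.9% | 14 |
| 0.30 | 72.2% | 85.4% | 13 |
| 0.35 | 84.5% | 94.0% | 10 |
| 0.40 | 92.5% | 98.0% | 6 |

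Over d from 0.20 to 0.40 and ρ from 0.3 to 0.7, the ANCOVA gain runs from about 3 points (d = 0.40, ρ = 0.3) to about 30 (d = 0.25, ρ = 0.7). Almost all of it comes from the baseline covariate: replacing the rank test by an unadjusted t-test gains only 1 to 2 points.

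**Step 3: 6 months.** The number with a 6-month visit depends on which description of the late enrollees is used.
- The synopsis and Section 3.2 refer to roughly the final quarter of enrollment. Read as 25%: 151.2 × 0.75 = 113.4 per arm.
- Section 3.0 refers to roughly the last 3 months. With 21 months of even accrual, 3/21 = 14%: 151.2 × 18/21 = 129.6 per arm.

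Both figures carry the month-3 missingness of 10% to month 6, which the documents do not state. At d = 0.30 and ρ = 0.5, with rank-based adjustment:
- 113.4 per arm: Φ(2.21 − 1.96) = 60% unadjusted; Φ(2.21/0.866 − 1.96) = 72% adjusted.
- 129.6 per arm: Φ(2.36 − 1.96) = 66% unadjusted; Φ(2.36/0.866 − 1.96) = 78% adjusted.

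**County adjustment.** The documents give nothing from which to size the gain from county alone, so no figure is given.

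**The case against.** The strongest reply is that the plan as written may have no baseline stigma score to adjust for. Table 3 gives stigma a 3- and 6-month time frame only, while the row for STI service delivery in the same table does name baseline. The baseline list in Section 6.1 omits stigma. The word repeat in Section 6.4 is thin evidence, because the follow-up surveys also carry material not listed at baseline, such as the System Usability Scale and the social-harm questions. This stands: baseline adjustment can be proposed only conditionally.

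A reader might go further and infer that the plan throws away an available baseline score and so loses about 10 points of power. The documents do not support that. A gain of about 10 points needs both ρ near 0.5 and unadjusted power near 80%, and neither is in the plan. Nor do the documents say how stable stigma scores are over time. Even the reading that only follow-up scores are tested is an inference, although it is the natural one for an outcome defined at 3 and 6 months.

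It can also be said that the Wilcoxon test is valid under randomization, suits a skewed score, and is accompanied by descriptive statistics and a weighting step for imbalance. Validity is granted. Descriptive summaries by arm are not a between-arm estimate with an interval. The weighting step is a sensitivity analysis triggered by observed imbalance, with no threshold or covariate list, so it does not replace a prespecified adjusted analysis.

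**Conclusion.** The point holds in limited form. For PrEP stigma, the plan specifies an unadjusted two-sample test that uses neither the county strata nor any baseline score, and it specifies no between-arm estimate with a CI. The missing estimate and the unused strata follow directly from Sections 3.2, 9.2 and 9.2.2 and need no assumption beyond treating the score as continuous.

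The power gain is conditional on a baseline score being collected and on assumed values of d, ρ and missingness, so it should be given only as the ranges worked out above.

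This concerns efficiency and interpretability for one secondary outcome. It does not make the stigma comparison invalid, and it does not touch the primary outcome or the go/no-go milestones. Priority is low.

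**What to change.** In Sections 9.2 and 9.2.2, for PrEP stigma at 3 and 6 months:

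1. Report the between-arm mean difference with a 95% CI from a regression of the score on arm and county, with robust standard errors. State in advance how sparse counties will be pooled.
2. State whether the stigma scale is in the baseline CASI. If it is, add the baseline score as a covariate. If it is not, only the county adjustment and the estimate with CI apply.
3. If the scores are expected to be skewed, rank ANCOVA on the same covariates is an alternative for the test.
4. Keep the Wilcoxon test as a sensitivity analysis, and say whether it uses follow-up or change scores.

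Make the change before outcome data are analyzed by arm, so that the choice of model is not driven by the results.

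The cost is some SAP wording and one regression per time point. The downsides are small: sparse county strata need pooling (15 counties were taking part in December 2023, with expansion from 2024), and participants without a baseline score need a simple fill-in, such as the overall mean with a missing indicator, to stay in the model. Without a baseline score, no new data are needed for the county-adjusted estimate.

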5.8 Participant Randomization

Participants will be randomized 1:1. Randomization procedures are automated through the study database. Randomization is completed after a participant has completed informed consent and their Baseline survey. Participants will be informed by study staff of their study condition assignment during their onboarding appointment. The study onboarding appointment is tailored to the study arm condition they are assigned (Figure 2).

Study staff are trained to follow similar protocol for scheduling, enrollment, and follow-up regardless of arm which includes the use of IRB-approved guides for participant communications and specified standard operating procedures for participant outreach mode, timing, and frequency. Communication attempts will be tracked in a communication log for prospective and enrolled persons. PIs and the study monitor will be able to see the records for all those who complete screening and could assess whether there is differential communication efforts or enrollment by randomization condition.

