7.0 OUTCOME MEASURES AND DATA SOURCES

For interventions that address systems-level challenges or utilize patient navigation as an intervention component, PrEP uptake is an appropriate primary outcome as it is an indication of the success of the intervention to overcome the barriers to access to the health service/treatment^{42,43}. Given the current lack of PrEP availability in the proposed study settings, an intervention that can overcome the multi-level barriers to PrEP access and uptake is a critical first-step.

With PrEP uptake as the primary outcome and the primary objective to increase PrEP uptake, this study will follow a similar operational definition as another large-scale mHealth RCT intervention for PrEP uptake among MSM in the southern United States⁴⁴: self-report taking any PrEP (oral or injection) on a follow-up survey or in the app, AND verified by at least one of the following: (1) an uploaded photo or image demonstrating a PrEP prescription; OR (2) any indication of the presence of tenofovir diphosphate or cabotegravir in DBS; OR (3) staff-abstracted electronic medical record of PrEP prescription issued or physician notation of PrEP initiated.

Table 3 presents the study Outcome Measures and their data sources.

| Table 3: Study Outcome Measures and Data Sources | | | |
|--|---------------------------------------|---|---|
| Name | Time Frame | Brief Description | Data sources |
| Primary outcome | | | |
| PrEP uptake | 3-month follow-up | Verified self-reported PrEP use (first dose, oral or injectable) ¹ | CASI, in-app report, EHR abstraction, self-collected lab sample |
| Secondary outcomes | | | |
| PrEP uptake | 6-month follow-up ⁴ | Verified self-reported PrEP use (first dose, oral or injectable) ¹ | CASI, in-app report, EHR abstraction, self-collected lab sample |
| PrEP care engagement | 3- and 6-month ⁴ follow-up | Daily oral or event driven PrEP: after PrEP uptake, number and dates of any subsequent PrEP visits or new/refilled | CASI, EHR |

| | | | |
|--|--|--|--|
| | | PrEP prescriptions Injectable PrEP : after initial injection, number and dates of any subsequent PrEP visits/injections | |
| PrEP use | 3- and 6-month ⁴ follow-up | Number of consecutive months PrEP used, based on date of first and last dose ² | CASI, EHR |

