*Assuming PrEP uptake of 2.5% in the control arm, 10% missing data at month 3, and 5% type I error

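### The only method named for count outcomes, exact Poisson regression, can give too many false positives for the secondary PrEP visit/refill count, and Section 9.2 has no dispersion check or fallback

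*Combined protocol and SAP*

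**What the plan says.** Section 9.2 (Outcome Analysis) assigns methods by outcome type: a probability difference for binary outcomes, the Wilcoxon rank-sum test for continuous ones, and for counts "we will use small analysis methods for count data (e.g. exact Poisson regression". Its illustration of a count is given as "data variables (e.g., number of unprotected sex acts". The sentence mentions no dispersion check, no robust variance and no alternative model.

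Section 9.2.2 carries this to the secondary outcomes: "All analyses will follow the specifications described above in 9.2". Table 3 in Section 7.0 lists PrEP care engagement among them. For oral PrEP it is defined as "after PrEP uptake, number and dates of any subsequent PrEP visits or new/refilled" prescriptions, with a parallel definition for injections, at 3 and 6 months. Table 3 does not say whether the arms are compared on this count over everyone randomized or only over those who started PrEP. It lists no sex-act count as an outcome.

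**The concern.** A Poisson model fixes the variance at the mean and treats every event as independent. In this context the word exact means only that no large-sample approximation is used. It gives no protection when the counts are not Poisson.

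PrEP visits over all randomized participants are a natural case for trouble. On the plan's own planning figures, 90% to 97.5% of each arm never starts PrEP and therefore contributes a zero. All events come from the remaining few, and a person with one later visit is likely to have another. The test then treats visits as its sample size when the independent units are people. At stake are the p-value and interval for a secondary claim that the intervention improves engagement in PrEP care.

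**Working it through.** The documents give no mean, variance or power for any count outcome, so there is no stated figure to reproduce. The check asks how far the named test departs from 5% when there is no true difference.

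**Inputs from the plan**
- Sample size: "The study will enroll for 21 months with a target sample size of 336". Allocation: "Participants will be randomized 1:1".
- Planning assumptions under Table 4: "Assuming PrEP uptake of 2.5% in the control arm, 10% missing data at month 3, and 5% type I error". This gives 336/2 × 0.9 = 151 analysed per arm.
- Uptake: 2.5% in control and 2.5% + 7.5% = 10% in the intervention arm. Under no difference, both arms are set at the midpoint, (2.5% + 10%)/2 = 6.25%, or 151 × 0.0625 = 9.4 starters per arm.
- Test level: 5%, two-sided, borrowed from the primary power calculation ("with a 5% type I error rate and a two-sided Chi-square test"). None is stated for count outcomes.

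**Assumed, not in the documents:** the number of later visits per starter, and the dispersion of any sex-act count.

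**Formulas.** Write φ for variance/mean. A nominal 5% Poisson test has true size of about 2 × (1 − Φ(1.96/√φ)), and its interval is 1/√φ of the correct width. If a share π starts PrEP and starters have visits with mean m and variance v, then φ over all participants is v/m + (1 − π)m. For exactly k visits each this is k(1 − π). For Poisson visits it is 1 + m(1 − π).

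**PrEP visits over all randomized, π = 6.25%, 151 per arm**

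| Later visits per starter | φ | Formula | Simulated exact test |
|---|---|---|---|
| Exactly 1 | 1 × 0.9375 = 0.94 | 4% | about 2% |
| Exactly 2 | 2 × 0.9375 = 1.88 | 15% | 12% |
| Poisson, mean 2 | 1 + 2 × 0.9375 = 2.88 | 25% | 21% |
| Poisson, mean 3 | 1 + 3 × 0.9375 = 3.81 | 32% | 29% |

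The simulated values are somewhat lower because an exact test on so few events is itself conservative. The result depends little on uptake. With 2.5% or 10% starting in both arms, exactly two visits gives 12% to 13% and Poisson mean 2 gives 20% to 23%. Intermediate patterns (Poisson mean 1, or two scheduled visits each attended with probability 0.7) give 9% to 13%.

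**PrEP visits among initiators only.** With 15 per arm and scheduled visits, φ is about 0.3 and the size is about 0%. With Poisson visits of mean 1 it is 2.9%. With 6.25% starting and Poisson visits of mean 2 or 3 it is 4.4%. All are below 5%.

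**Sex acts, if analysed.** With negative binomial counts at φ = 2, 5 and 10, the formula gives 17%, 38% and 54%. Simulation gives 16%, 36% to 38%, and 53% to 54%. At φ = 1 the same test gives 4.3%, so the excess comes from dispersion and not from the test procedure.

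**The alternatives.** Under the visit patterns in the table and the same three sex-act settings, Poisson regression with robust standard errors and a participant-level permutation test of the difference in mean counts both stayed at about 3% to 6%. With only 151 × 0.025 = 3.8 starters per arm they were at or below 5%, at times well below. In that setting the chance that an arm has no starter is 0.975^151 = 2.2%, so in about 4% of trials at least one arm has no events and no rate ratio can be estimated. The permutation test still works there. The permutation check was run without county strata.

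**The case against.** Several points on the other side stand.

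- A reader might infer that the plan commits every count to exact Poisson regression. It does not: the method is given as an example. It is, however, the only one named, and nothing says when another would be used.
- A reader might infer that the counts are known to be strongly over-dispersed. The documents report no dispersion for any count, and for visits the direction can reverse. If visits follow a quarterly rhythm, a 3-month count may hold at most one later visit per starter, and the test is then conservative. Table 3 counts visits after uptake, which can be read as initiators only, and that reading is conservative too in the patterns tried. But starting PrEP is itself affected by the intervention, so an initiators-only comparison gives up the protection of randomization.
- The largest percentages belong to sex acts, and no sex-act count is a Table 3 outcome. Sexual behaviour enters only self-reported event-driven adherence and the exploratory effective-protection proportions.
- A reader might infer from the 30- and 75-day figures for the 3-month survey (Tables 2.2 and 2.3) that follow-up time differs and is ignored. Those are windows for completing the survey. They are set by enrolment period and balanced between arms by randomization, so they add little.
- Negative binomial regression with county terms, the textbook remedy, is fragile here. In 400-run simulations with about 19 starters and an assumed 15 equal counties, it failed to converge in 38% to 48% of runs. It should not be the default.

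**Conclusion.** The point holds as a secondary-analysis issue of minor to moderate weight. For the PrEP visit/refill count, the true error rate of the named method runs from about 2% to about 29% when all randomized participants are compared. Where it falls depends on the visits per starter, which are assumed here, and on an analysis set that the plan leaves open. The rate exceeds 5% once starters typically have more than one later visit, and reaches 12% to 29% at about two or more. Any sex-act count would be exposed only if it is analysed and over-dispersed.

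The documents do not support extending this to the trial's main conclusions. The primary outcome is binary and analysed as a difference in proportions. Milestones 5 and 6, the effectiveness criteria for Go/No-Go, are also proportions.

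**What to change.** In Section 9.2, replace exact Poisson regression with Poisson regression using robust (sandwich) standard errors. When events are sparse, use a permutation test of the difference in mean counts, stratified by county to match the randomization, with the participant as the unit. Define sparse in advance by the number of participants with a non-zero count, and include the case where one arm has no events. Both methods hold close to 5%, or below it when starters are very few, whether counts are over- or under-dispersed.

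In Section 9.2.2 or Table 3, state that the PrEP visit/refill count is compared across all randomized participants, with non-starters counted as zero, and say which other outcomes, if any, are treated as counts.

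The cost is a few sentences and no new data. Intervals for over-dispersed counts become wider by a factor of √φ: about 1.4 at φ = 1.88 and 2.0 at φ = 3.81. That is the width they should have had.
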